### 9.2.3 Estimands for Primary Safety Analyses for Phase 1/2/3a, Phase 3b, Phase 3c and Pooled Cohorts

Estimand Label	Estimand 3 (Safety – Unsolicited AEs/AEs leading to discontinuation or withdrawal/MAAE/SAE)
Estimand Description	
Count and percentage of vaccinated participants who would develop unsolicited AEs, AEs leading to discontinuation/withdrawal, MAAEs, and SAEs.
 
These will be evaluated with each dose of study vaccine, ARCT-154 or placebo.

Target Population	The population who are enrolled in the study and receive any dose of study vaccine

Endpoint	Occurrence of unsolicited AEs will be analyzed up to 28 days after each study vaccine administration.  Occurrence of AEs leading to discontinuation/withdrawal, MAAEs, or SAEs will be analyzed up to Day of Switchover/Further Study Vaccine, receipt of non-study vaccine, early withdrawal, or last on-study assessment visit, whichever comes first.  Occurrence of AEs leading to discontinuation/withdrawal, MAAEs and SAEs after the Switchover/Further Study Vaccine will be recorded and summarized for the interval from the switchover/Further Study Vaccine up to Day 394 (Phase 1/2/3a and Phase 3b only).  For Phase 1/2/3a and 3b, AEs in participants who do not undergo Switchover/Further Study Vaccine will be recorded for the interval from Day 92 up to Day 394
Treatment Conditions	Phase 1/2/3a and 3b: ARCT-154 dose 5 µg or placebo administered on Day 1, Day 29, or at Switchover/Further Study Vaccine (Day 92 and Day 120)  Phase 3c: ARCT-154 dose 5 µg or ChAdOx1 administered on Day 1 and Day 29.
Population-Level Summary	Percentage of vaccinated participants who develop each type of AE
Intercurrent Event (IcEv) Strategy	
IcEv1 (Death not due to COVID-19)	Composite strategy
IcEv2 (Non-study vaccine)	While on treatment strategy
IcEv3 (Early infection)	Composite strategy

IcEv4 (Study infection)	Composite strategy
IcEv5 (Confounding On-study Medications)	treatment policy strategy
Rationale for Strategies	Events occurring after IcEv2 could contribute spurious safety data so a while on treatment policy is used for these events and events occurring after this IcEv's will be summarized separately.
Estimand Label	Estimand 4 (Reactogenicity – Solicited AEs)
Estimand Description	Count and percentage of vaccinated participants who would develop solicited AEs. These will be evaluated after vaccination on Day 1 and Day 29, ARCT-154 or placebo.
Target Population	Vaccinated adults providing at least 1 Diary assessment, including reported absence of solicited events.
Endpoint	Occurrence of solicited AEs: Solicited AEs within 7 days after study vaccination on Day 1 and Day 29, by Toxicity Grade
Treatment Conditions	Placebo or ARCT-154 at dose 5 µg administered on Day 1 and Day 29.
Population-Level Summary	Percentage of vaccinated participants who provide at least 1 safety assessment.
Intercurrent Event (IcEv) Strategy	
IcEv1 (Death not due to COVID-19)	Treatment policy strategy
IcEv2 (Non-study vaccine)	Treatment policy strategy
IcEv3 (Early infection)	Treatment policy strategy

IcEv4 (Study infection)	Composite strategy
IcEv5 (Confounding Concomitant Medications)	Treatment policy strategy
Rationale for Strategies	A treatment policy strategy is used for assessing safety irrespective of occurrence of IcEv2, IcEv3, IcEv5

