3.3 Phase 3c Substudy

3.3.1 Phase 3c Substudy Primary Objectives and Endpoints

The primary objectives and endpoints for Phase 3c are presented in [Table 8](#). The first approximately 1,500 participants in Phase 3c will be enrolled into Phase 3c-1, the group that will have blood drawn for immunogenicity assessments. Data from 800 participants in this subgroup will be used to establish the noninferiority of immunogenicity of ARCT-154 vaccine as compared to ChAdOx1. Samples from the remaining 700 participants in Phase 3c-1 will be retained for potential future immunological testing, for example against newly emerging variants of concern. Safety evaluations will be based on all participants in Phase 3c.

Table 8 Phase 3c Substudy Primary Objectives and Endpoints

Phase 3c Primary Objectives	Endpoint Description
1. To assess the safety and reactogenicity of ARCT-154 and ChAdOx1	
Safety will be evaluated in all participants in the Phase 3c SAS and will be summarized for each vaccination as number and percentage of participants with:
 
 • Any unsolicited AE starting within 28 days after each study vaccine administration, summarized by severity and relationship to study vaccine. • Any medically attended adverse event (MAAE), serious adverse event (SAE), or AE leading to discontinuation/withdrawal through Final Visit/Early Termination (ET) summarized by relationship to study vaccine. 
Reactogenicity will be evaluated in participants in the Phase 3c RAS and will be summarized following vaccinations on Day 1 and Day 29 only as the number and percentage of participants with:
 
 • Any solicited local or systemic AE starting within 7 days after each study vaccine administration by toxicity grade.

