8.9.3 Phase 3c Substudy

The primary Phase 3c analysis of safety will be performed when all participants have reached the last study visit (Day 394).

The primary immunogenicity non-inferiority analysis for Phase 3c-1 will be performed after all participants in this cohort reach the Day 57 timepoint.

Interim analysis of safety data through at least Day 57 may be performed for Phase 3c at the time of analysis of the primary immunogenicity non-inferiority endpoint of Phase 3c-1 to support regulatory submission.

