**Table 3 Phase 3c Objectives and Endpoints**

Phase 3c Primary Objectives	Endpoint Description
1. To assess the safety and reactogenicity of ARCT-154 and ChAdOx1	
Safety:
 
 
Any unsolicited adverse events (AE) starting within 28 days after each study vaccine administration, summarized by severity and relationship to study vaccine.
 
Any medically attended adverse event (MAAE), serious adverse event (SAE), or AE leading to discontinuation/withdrawal through Final Visit/Early Termination (ET) summarized by relationship to study vaccine.
 
 
Reactogenicity following vaccinations on Day 1 and Day 29 only:
 
 
Any solicited local or systemic AE starting within 7 days after each study vaccine administration by toxicity grade.
 

2. To evaluate noninferiority of neutralizing antibody (NAb) geometric mean concentration for ARCT-154 versus ChAdOx1 at Day 57	
NAb responses by pseudovirus microneutralization test (MNT) evaluated at Day 57 for assessment of geometric mean concentration.
 
 
The endpoint is the geometric mean ratio of the surrogate virus neutralization test for ARCT-154 and ChAdOx1 at Day 57
 

Phase 3c Secondary Objectives	Endpoint Description
1. To evaluate noninferiority of IgG binding antibody geometric mean concentration for ARCT-154 versus ChAdOx1 at Day 57	
IgG antibody binding the full-length SARS-CoV-2 spike protein (binding antibody [BAb]) responses evaluated at Day 57 for assessment of geometric mean concentration.
 
 
The endpoint is the geometric mean ratio of BAb for ARCT-154 and ChAdOx1 at Day 57
 

2. To evaluate noninferiority of neutralizing antibody (NAb) seroconversion rate for ARCT-154 versus ChAdOx1 at Day 57	
NAb responses by pseudovirus microneutralization test (MNT) evaluated at Day 1 (baseline) and Day 57 for assessment of seroconversion.
 
 
The endpoint is seroconversion rate (defined as: 4-fold increase in titer from baseline) for ARCT-154 and ChAdOx1 at Day 57
 

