### 6.6.1.3 Serious Adverse Events and other Events

SAEs, MAAEs, AEs leading to withdrawal of vaccine and AEs leading to study discontinuation will be summarized in the same manner as unsolicited AEs:

- Overview table
- Events by SAE criteria (only applicable for SAEs)
- Summary by SOC and PT
- Summary by PT
- Summary by SOC, PT and Severity
- Summary of related events by SOC and PT
- Summary of related events by SOC, PT and severity

SAEs with fatal outcome will be summarized by SOC and PT.

SAEs, MAAEs, AE leading to discontinuation and AEs with fatal outcome will be summarized for the following analysis sets and time intervals:

Analysis set	Time interval
Phase 1/2/3a SAS	

• From Day 1 to Day 92 (for participants without Switchover/Further study vaccine) or Switchover/Further study vaccine . Percentages will be computed based on the number of participants in SAS who received at least one dose of study vaccine during reporting period (i.e a dose at Day 1 or at Day 29).

• From Switchover/Further study vaccine to End of study, for participants with Switchover/Further study vaccine. Percentages will be computed based on the number of participants in SAS who received at least one dose of study vaccine during reporting period (i.e a dose at Day 92 or at Day 120).

• From Day 92 to End of Study, for participants without Switchover/Further study vaccine. Percentages will be computed based on the number of participants in SAS still on study at Day 92 and without Switchover or further study vaccine.

• From the first dose of ARCT-154 vaccine administration to End of Study. Percentages will be computed based on the number of participants in SAS who received at least one dose of ACRT154 study vaccine.

Phase 3b SAS	
Phase 3c SAS	

• From Day 1 to Day 92. Percentages will be computed based on the number of participants included in Phase 3c SAS.

---

	

• From Day 92 to End of Study. Percentages will be computed based on the number of participants included in Phase 3c SAS.

Pooled SAS	From Day 1 to Day 92 (for participants without Switchover/Further study vaccine) or Switchover/Further study vaccine (main estimation). Percentages will be computed based on the number of participants in Pooled SAS who received at least one dose of study vaccine during reporting period (i.e Day 1 or Day 29).

---

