Section 8.7.2 Table 18 estimand 2 (efficacy)	Imputation/Data/Censoring Rules: For deaths unrelated to COVID-19, censor at date of death. For participants who undergo Switchover/Further Study Vaccine or receive a non-study COVID-19 vaccine, censor at date of Switchover or non-study vaccination.	Participants last date at risk date will also be censored for Lost to Follow-up	Add rule of handing censoring condition for lost to follow-up scenario.
Section 8.7.2 Table 18 estimand 2 (efficacy)	Sensitivity: the same analysis will be performed in the Pooled mITT and Phase 3b PP analysis sets.	
2 additional sensitivity analyses to be performed.
 
 
• A sensitivity analysis of all Covid cases reported in CRF and not confirmed by the blinded Independent Adjudication Committee or with severity as reported in the CRF has been added for the primary endpoint, severe cases and deaths due to COVID-19.
 
• Day 36 is defined as second dose+7 days (29+7=36 days), and Day 92 is defined as second dose+63 days (29+63=92 days). Another sensitivity analysis of the primary endpoint (Phase 3b only) will be performed using Day 92 visit instead of second dose+63 days.
 
	Add additional sensitivity analyses to assess the robustness of the primary analysis results.
Section 8.7.2 Table 18 estimand 3 (safety)	Supportive: Analysis will be performed for different time intervals, specifically:	As per section 6.6.1.3 of this SAP, only the following intervals will be done:	To summarize study periods that are not overlapping

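### Phase 3c has no planned by-arm table of SAEs, MAAEs and discontinuation AEs over the whole follow-up, and the documents state two different windows for that endpoint

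*SAP*

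**What the plan says.** **The endpoint.** Phase 3c primary objective 1 in SAP Table 3 has three components: solicited AEs within 7 days of a dose, unsolicited AEs within 28 days of a dose, and any MAAE, SAE or "AE leading to discontinuation/withdrawal through Final Visit/Early Termination (ET) summarized by relationship to study vaccine". Protocol 3.3.1 (Table 8) has the same end point for the third component: "or AE leading to discontinuation/withdrawal through Final Visit/Early Termination (ET) summarized by relationship to study vaccine".

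**The estimand.** For that third component SAP 9.2.3 states: "SAEs will be analyzed up to Day of Switchover/Further Study Vaccine, receipt of non-study vaccine, early withdrawal, or last on-study assessment visit". The earliest of these applies. Protocol 4.4 and SAP 2.2 say Phase 3c has no switchover, so only non-study vaccine, early withdrawal or the last visit can end the window there.

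**The timing.** Protocol 8.9.3: "The primary Phase 3c analysis of safety will be performed when all participants have reached the last study visit (Day 394".

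**The planned tables.** SAP 6.6.1.3 gives the Phase 3c safety set two intervals: "From Day 1 to Day 92. Percentages will be computed based on the number of participants included in Phase 3c SAS" and "From Day 92 to End of Study. Percentages will be computed based on the number of participants included in Phase 3c SAS". The one interval in that section that runs across Day 92 starts at the first ARCT-154 dose. It belongs to the Phase 1/2/3a and 3b block and takes ARCT-154 recipients as its denominator.

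**The restriction.** The SAP 7.1 entry on Estimand 3 in protocol Table 18 limits output to the intervals of 6.6.1.3. Its reason is "To summarize study periods that are not overlapping". The protocol had listed a cumulative interval to Day 394 among its supportive analyses.

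**The other window.** Protocol Table 18 describes Estimand 3 as ending at the earlier of Day 92/switchover or non-study vaccine, with the Phase 3c safety set among its analysis sets. SAP Table 8 uses a Day 92 limit in a row that also names the Phase 3c safety set.

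**The concern.** The estimand's summary measure is the percentage of participants who develop each type of AE, which means one count per participant over the whole window. Two tables cut at Day 92 do not supply that. The reason given for dropping the longer interval suits the parts in which treatment changes at Day 92. In Phase 3c nothing is given at Day 92, which is a scheduled telephone call, and the list in SAP 7.1 is built around switchover and does not mention the Phase 3c endpoint.

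This matters more in Phase 3c than elsewhere. SAP 7.1 drops its immunogenicity and efficacy analyses, so safety is its only primary objective still analysed. It is also the only part in which the randomised groups are not given a different vaccine at Day 92. At stake is whether a reader can see, for ARCT-154 and for ChAdOx1, the proportion of participants with an SAE, MAAE or discontinuation AE over the period that the objective names.

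**Working it through.** **1. The plan's own figure.** The only number attached to Phase 3c safety is the probability of seeing at least one event, p = 1 − (1 − R)^N (SAP 6.1). With R = 0.001 and N = 1,200, p = 1 − 0.999^1200 = 0.699, the stated 69.9%. With R = 0.01, p = 0.999994, consistent with the stated figure of more than 99%. Both reproduce, and this point does not change them.

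**2. Window against output for the long-term component, Phase 3c.**

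| Source | End of window |
|---|---|
| SAP Table 3; protocol Table 8 | Final visit or early termination |
| SAP 9.2.3; protocol Table 17 | Earliest of non-study vaccine, withdrawal, last visit (no switchover) |
| Protocol 8.9.3 (timing of analysis) | Day 394 |
| Protocol Table 18; SAP Table 8 | Day 92 or non-study vaccine |
| SAP 6.6.1.3 (tables planned) | Day 1–92, and Day 92–end of study |

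The Day 1–92 table serves the fourth row. No table serves the first three. Other outputs do not fill the gap:

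- The overview in SAP 6.6.1.2 counts SAEs and MAAEs, but only within 28 days of a dose.
- SAP Table 8 has a second row for further time intervals, but it names none; 6.6.1.3 names them.
- The listings give no rates by arm.
- Extending the interval from first ARCT-154 dose to Phase 3c would give no ChAdOx1 column.

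**3. What the two tables determine.** Both use the Phase 3c safety set as denominator. Let p1 and p2 be the percentages with an event in each interval and p12 the percentage with an event in both. The cumulative percentage is

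p = p1 + p2 − p12, with 0 ≤ p12 ≤ min(p1, p2) when p1 + p2 ≤ 100%.

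Hence max(p1, p2) ≤ p ≤ p1 + p2, a range of width min(p1, p2). The documents give no rates, so the rows below are assumptions, with 1,200 per arm.

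| p1 | p2 | Range for p | Participants |
|---|---|---|---|
| 2% | 2% | 2% to 4% | 24 to 48 |
| 10% | 10% | 10% to 20% | 120 to 240 |
| 10% | 15% | 15% to 25% | 180 to 300 |
| 10% | 20% | 20% to 30% | 240 to 360 |

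If events in the two periods were independent, the 10%/15% case would give 1 − 0.90 × 0.85 = 23.5%. The tables cannot show whether they are. If both arms showed 10% and 15%, the cumulative difference between arms could in principle lie anywhere from 15 − 25 = −10 to 25 − 15 = +10 percentage points. These are extreme limits, not expectations.

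**4. Boundary.** As written, Day 92 belongs to both Phase 3c intervals, so they are not strictly non-overlapping either.

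**The case against.** The strongest reply is that little is lost. The solicited and 28-day unsolicited components of the objective are tabulated for Phase 3c (SAP Table 8, 6.6.1.1, 6.6.1.2). The two long intervals share a denominator and together span all follow-up, SAEs and MAAEs are listed, and events after a non-study vaccine get their own summary. All of this stands. A reader might infer that the Phase 3c primary safety endpoint is not reported at all, or that late events disappear. The documents do not support that: the missing item is the cumulative by-arm participant percentage for one component.

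Second, the Day 92 split may be deliberate. Protocol Table 18 and SAP Table 8 use Day 92, the Phase 3c visit schedule is divided there, the Day 394 interval was only supportive in Table 18, and SAP 7.1 discloses the restriction with a reason. This stands as evidence that the documents disagree, so it cannot be said that every passage runs Estimand 3 to the last visit. It does not settle the matter for Day 92. Table 18 refers the reader to Table 17 for the full definition, and Table 17 has the last-visit wording. The 7.1 entry changes supportive intervals and does not amend the objective in SAP Table 3.

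Third, a reader might infer a loss of power from splitting the period. That does not apply. Protocol 8.4.3 and SAP 6.2.3 plan no safety test for Phase 3c, and SAP 7.2 removes confidence intervals for AE incidence.

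Fourth, it would be too strong to treat all of Phase 3c as a complete comparison to Day 394. Estimand 3 stops at non-study vaccine, protocol 8.5.3 allows for 20–25% dropout because of the national vaccination campaign, and SAP 7.1 cites routine vaccination as a reason not to analyse Day 394 immunogenicity samples in Phase 1/2/3a.

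**Conclusion.** The point holds for the long-term component of Phase 3c primary safety objective 1. Followed as written, the SAP never gives, by arm, the percentage of participants with an SAE, MAAE or discontinuation AE from Day 1 to the end of the window in SAP Table 3 and SAP 9.2.3. The two planned percentages leave that figure uncertain by up to the smaller of the two: 2 percentage points at 2% and 2%, 10 at 10% and 15%. Those rates are assumed; the bound itself is not. Separately, the documents state two windows for the same component, last visit and Day 92, without reconciling them.

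This is a reporting gap of moderate weight. No hypothesis test depends on it and no follow-up period is left untabulated. It should still be corrected, because it concerns the only primary objective of Phase 3c that is still analysed and the correction is cheap.

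**What to change.** 1. In SAP 6.6.1.3, add an interval for the Phase 3c safety set, by arm: Day 1 to end of study, cut at receipt of a non-study COVID-19 vaccine, each participant counted once. Apply it to SAEs, MAAEs, AEs leading to discontinuation and fatal AEs, including the summaries by relationship. Name it as the table that reports the SAP Table 3 endpoint.
2. Keep the two existing intervals, and assign Day 92 to one of them.
3. Reconcile SAP Table 8, the Table 18 entry in SAP 7.1 and Estimand 3 in SAP 9.2.3 so that one window is stated for Phase 3c. Record in 7.1 that the non-overlap reason applies to the parts with a vaccine change at Day 92.

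The cost is a few more output tables from shells already planned, with no new data. SAP 2.4 says Phase 3c was still blinded while this SAP was being developed, so a change made before that part is unblinded would not be informed by its results.

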### 9.3 Overview of assay and available analyzed samples by phase

Lab.	Assay		Timepoints
NIHE	Serum NAb titer against SARS-CoV-2	Genscript SARS-CoV-2 surrogate virus neutralization test (sVNT)	
 
Phase 1: at Day 1, Day 29, Day 57, Day 92
 
Phase 2: at Day 1, Day 29, Day 57, Day 92, D120
 
Phase 3a: at Day 1, Day 29, Day 57, Day 92, D120
 

		plaque reduction neutralization test (PRNT50) (live virus assay) : 
 
- Ancestral-clinical isolate variant
 
- Delta-clinical isolate variant
 
	
 
Phase 1: at Day 1, day 29, Day 57
 
Phase 2: at Day 1, day 29, Day 57
 
Phase 3a: no data available
 

	Serum IgG antibodies binding (bAB) the SARS-CoV-2 spike protein-Siemens Advia platform		
 
Phase 1: at Day 1, Day 29, Day 57, Day 92
 
Phase 2: at Day 1, Day 29, Day 57, Day 92, D120
 
Phase 3a: at Day 1, Day 29, Day 57, Day 92, D120
 

PPD	Serum NAb titer against SARS-CoV-2: Pseudovirus microneutralization test (MNT)	Ancestral-Hu-1 [D614G variant (VAC62 validated)]	
 
Phase 1: Day 1 and Day 57
 
Phase 2: Day 1 and Day 57, Day 92 and D120
 
Phase 3a: Day 1 and Day 57, Day 92 and D120
 

		Delta variant (VAC120 )	
 
Phase 1: no data available
 
Phase 2: Day 1 and Day 57, Day 92 and D120
 
Phase 3a: Day 1 and Day 57, Day 92 and D120
 

		Omicron BA.1 variant (VAC122 validated)	
 
Phase 1: no data available
 
Phase 2: Day 1, Day 57, Day 92, Day 120
 
Phase 3a: Day 1, Day 57, Day 92, Day 120
 

	- S		
 
Phase 1: at Day 1 and Day 57
 

	ACE2 receptor binding inhibition sVNT assay: multiplex neutralization assay (VAC114)	- S_B.1.1.7 - S_B.1.351 - S_B.1.526.1 - S_B.1.617 - S_B.1.617.1 - S_B.1.617.2 - S_B.1.617.3 - S_P1 - S_P2	
 
Phase 2: at Day 1 and Day 57
 
Phase 3a: no data available
 

	Serum IgG antibodies binding the SARS-CoV-2 spike : Mesoscale Discovery (MSD) multiplex assay	- Spike (S) - Receptor binding domain (RBD) - Nucleocapsid (N)  (antigens of the Ancestral variant SARS-CoV-2)	
 
Phase 1: at Day 1 and Day 57
 
Phase 2: at Day 1 and Day 57
 
Phase 3a: no data available
 

## 9.4 Laboratory Conversion Factors

G/L original unit corresponds with 10^9/L SI unit for white blood cells and platelets. No other conversions are needed.

The conversion factor relating IU/mL to AU/mL for NAb by MNT assay, D614G variant is 1 IU/mL = 1.275 AU/mL.

The conversion factor relating IU/mL to AU/mL for NAb by sVNT (NIHE) is 1 IU/ml=Titer (AU/ml)/12.3

The conversion factor relating BAU/mL to AU/mL for Serum IgG antibodies binding the SARS-CoV-2 spike, MSD multiplex assay, Spike antigen is 1 BAU/mL = 0.00901\*(AU/mL).

The conversion factor relating BAU/mL to AU/mL for Serum IgG antibodies binding the SARS-CoV-2 spike, MSD multiplex assay, RBD antigen is 1 BAU/mL = 0.0272\*(AU/mL).

## 9.5 Example SAS code

### Time to Event/Hazard Ratio used for VE%:

```
proc phreg data=;
  class Treatment(ref='Placebo') Risk_group site_region;
  model aval*cnsr(1) = Treatment Risk_group site_region;
  estimate 'HR' Treatment 1 /exp cl;
  ods output estimates=est;
run;
```

### Categorical 95% CIs:

```
proc freq data=;
  by treatment;
  table <response>/bin(CL=CLOPPERPEARSON);
run;
```

